10.6. Insurance and Compensation for Injury

The Sponsor has covered this clinical study by means of an insurance of the clinical study according to national requirements. The name and address of the relevant insurance company, the certificate of insurance, the policy number and the sum insured are provided in the Investigator's Site File.

10.7. Protocol Approval and Amendment(s)

Before the start of the clinical study, the clinical study protocol and other relevant documents will be approved by the IRB/IEC, in accordance with local legal requirements. The Sponsor must ensure that all ethical and legal requirements have been met before the first subject is enrolled in the clinical study.

This protocol is to be followed exactly. To alter the protocol, amendments must be written, which must be released by the responsible staff and receive IRB/IEC approval prior to implementation (as appropriate).

Administrative changes may be made without the need for a formal amendment but will also be mentioned in the integrated CSR. All amendments will be distributed to all study protocol recipients, with appropriate instructions.

10.8. Confidentiality Data Protection

All clinical study findings and documents will be regarded as confidential. Study documents (protocols, IBs and other material) will be stored appropriately to ensure their confidentiality. The Principal Investigator and members of his/her research team (including the IRB/IEC) must not disclose such information without prior written approval from the Sponsor, except to the extent necessary to obtain informed consent from subjects who wish to participate in the study or to comply with regulatory requirements.

The anonymity of participating subjects must be maintained. Subjects will be specified on study documents by their subject number, initial or birth date, not by name. Documents that identify the subject (e.g., the signed ICF) must be maintained in confidence by the Principal Investigator.

10.9. Publication Policy

By signing the clinical study protocol, the Principal Investigator agrees with the use of results of the clinical study for the purposes of national and international registration, publication and information for medical and pharmaceutical professionals. If necessary, the regulatory authorities will be notified of the Principal Investigator's name, address, qualifications and extent of involvement.

A Principal Investigator shall not publish any data (poster, abstract, paper, etc.) without having consulted with the Sponsor in advance.

12. APPENDIX

Protocol: AARD-201
IRB# 210210
PI: [name]

MMTT

Date: ___ / ___ / ___

Subject #: _____

Subject Initials: ___ ___

Body Composition		
Time: _____		
Height: _____ cm	Weight: _____ kg	BMI: _____
Body Fat Percentage: _____ %		
Study Staff Initials and Date: _____		

Vital Signs	
BP and Heart Rate will be measured in the sitting position. The subject MUST be rested for at least 5 min.	
Time Subject Starts Resting: _____ : _____	
Arm (circle): LEFT RIGHT	
Time: _____	Blood Pressure: _____ / _____ mmHg Heart Rate: _____ bpm
Any repeat measurements of both the BP and heart rate must be taken at least 2 min. apart and recorded.	
Time: _____	Blood Pressure: _____ / _____ mmHg Heart Rate: _____ bpm
Respiratory Rate: _____ breaths/minute	Body Temperature: _____ °C
Study Staff Initials and Date: _____	

AE/SAEs & Concomitant Medications	
Did subject have any changes to their current medications? *If yes, note changes on the concomitant medication log.	 YES*  NO
Did subject report any adverse events or study related problems? *If yes, note changes on the AE/SAE log.	 YES*  NO
Study Staff Initials and Date: _____	

Baseline	
Did subject fast 10 hours as instructed? Date of last meal: ____/____/____ Time of last meal: ____ : ____	 YES  NO
Insert IV draw line into a peripheral arm vein approximately one hour before first draw.	
Study Staff Initials and Date: _____	

Mixed Meal Tolerance Test (MMTT)					
SCHEDULED Timepoint	Target time (hh:mm)	ACTUAL TIME (hh:mm)	Sample(s) collected/ Tasks	YSI Glucose reading (at each time point) YSI# _____	Nurse initials
-120 min			Instruct subject to empty bladder.		
-80 min			Start IDC #1: _____		
-50 min			Stop IDC #1: _____		
-30 min			Study Drug Given IF SECOND MMTT Time: _____		
-15 min			 Glucose  FFA  CCK  GIP  Insulin  Glucagon  PYY  GLP-1  C-Peptide  Ghrelin  Amylin		
-5 min			 Glucose  Insulin  C-Peptide  Cytokine panel  Bile Acids/Ferritin/CRP  Leptin/Adiponectin  6 ml Serum storage  6 ml Plasma storage		
0 min			Give Ensure liquid meal (2x Ensure) Consume within 5 minutes Start Time: _____ Stop Time: _____		

15 min			 Glucose  Insulin  C-Peptide  4 ml Serum storage  4 ml Plasma storage								
30 min			 Glucose  Insulin  C-Peptide  4 ml Serum storage  4 ml Plasma storage								
60 min			
 
  Glucose	 Insulin	
 
  C-Peptide	 FFA	
 
  4 ml Serum storage  4 ml Plasma storage	
 
	 Glucose	 Insulin	 C-Peptide	 FFA	 4 ml Serum storage  4 ml Plasma storage			
 Glucose	 Insulin										
 C-Peptide	 FFA										
 4 ml Serum storage  4 ml Plasma storage											
SCHEDULED Timepoint	Target time (hh:mm)	ACTUAL TIME (hh:mm)	Sample(s) collected/ Tasks	YSI Glucose reading (at each time point) YSI# _____	Nurse initials						
90 min			 Glucose  Insulin  C-Peptide  4 ml Serum storage  4 ml Plasma storage								
120 min			 Glucose  FFA  CCK  GIP  Insulin  Glucagon  PYY  GLP-1  C-Peptide  Ghrelin  Amylin  6 ml Serum storage  6 ml Plasma storage								
150 min			 Glucose  Insulin  C-Peptide  4 ml Serum storage  4 ml Plasma storage								
180 min			
 
  Glucose	 FFA	
 
  Insulin	 C-Peptide	
 
  4 ml Serum storage  4 ml Plasma storage	
 
	 Glucose	 FFA	 Insulin	 C-Peptide	 4 ml Serum storage  4 ml Plasma storage			
 Glucose	 FFA										
 Insulin	 C-Peptide										
 4 ml Serum storage  4 ml Plasma storage											
195 min			Start IDC #2: _____								
210 min			 Glucose  Insulin  C-Peptide  4 ml Serum storage  4 ml Plasma storage								
225 min			Stop IDC #2: _____								

240 min			 Glucose  FFA  CCK  GIP  Insulin  Glucagon  PYY  GLP-1  C-Peptide  Ghrelin  Amylin  4 ml Serum storage  4 ml Plasma storage		
AFTER final blood draw, remove IV.					
Nurse completing procedure Signature and Date: _____					
Attending Physician (PI/Sub-I) Signature and Date: _____					

Post-Procedure					
Post procedure meal eaten?	 YES	 NO	Time: _____		
Post-Procedure Glucose Check? mg/dL	 YES	 NO	Time: _____	BG: _____	
_____ mg/dL			Time: _____	BG:	
Any Adverse Events to report during or after study procedure?  YES*  NO					
*If yes, please describe below:					
Study Staff Initials and Date: _____

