Denatonium is one of the bitterest tastants among tens of thousands of natural or synthesized bitter compounds, with a bitterness detection threshold of 0.05 ppm. To date, one of the denatonium salts, denatonium benzoate has been approved as an additive to household products to prevent the ingestion of potentially harmful substances through taste aversion (Sibert JR and Frude N 1991). Importantly, the US Consumer Product Safety Commission has judged denatonium benzoate as generally safe. Like other bitter compounds, denatonium can strongly activate up to 25 G-protein coupled receptors expressed in a variety of tissues and organs including GI tract, pancreas, fat, trachea, and central nervous system. Bitter taste receptors are thought to be evolutionarily

conserved for the detection of potentially toxic compounds. Activation of bitter receptors in the mouth elicits a familiar aversive sensation, while activation of bitter receptors in the gut and chemoreceptor trigger zone located in the medulla leads to reduction of appetite and delayed gastric emptying as well as other adaptations. In a number of animal studies, denatonium benzoate has been shown to inhibit ongoing ingestive behavior, suppress food intake, and inhibit gastric emptying (Janssen S et al. 2011; Schier LA et al. 2011). Moreover, denatonium benzoate can stimulate the release of GLP-1 and CCK that are known to cause satiety and satiation (Chen MC et al. 2006; Kim KS et al. 2014). In human studies, the intragastric administration of denatonium benzoate after a liquid meal has been reported to inhibit relaxation of the proximal stomach. While in an oral nutrient tolerance test, denatonium benzoate was shown to increase satiation (Avau B et al. 2015). In a clinical trial conducted in healthy female volunteers, intragastric administration of denatonium benzoate is shown to decrease both antral motility and hunger ratings during the fasting state, probably via inhibiting motilin release. More importantly, no adverse reactions have been reported in all these human studies (Deloose E et al. 2017). Taken together, intragastric administration of denatonium salts is safe and can lead to weight loss by changing the appetite and eating behaviors and therefore, are promising agents for the treatment of obesity.

Rationale of the Study

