5. STUDY POPULATION

The study population will consist of male and female subjects at least one year after sleeve gastrectomy or gastric bypass surgery). Subjects must be able to provide written informed consent and meet all the inclusion criteria and none of the exclusion criteria.

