6.9. Special Precautions and Management of AEs

6.9.1. Eating disorders

ARD-101 may decrease appetite and subsequently change a subject's eating behavior by delaying gastric emptying and inducing the glucagon-like peptide-1 and cholecystokinin secretion into the circulation that targets the central nervous system (CNS) to cause satiety/hunger sensation. Subjects who develop any eating disorders during study treatment should be permanently discontinued from study drug.

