8.2.7. Mixed Meal Tolerance Test (MMTT)

The MMTT permits measurement of intestinal (incretin secretion), β -cell (insulin secretion), hepatic (insulin extraction), muscle, and adipose tissue responses to ingesting calories. The mixed meal, containing glucose, fat and protein (2x Ensure 8 oz. for a total of 16 oz., 66 grams carbohydrate (CHO), 440 calories), is more physiologic than the glucose only challenge in an oral glucose tolerance test (OGTT). The MMTT will be performed at the time points detailed in the Schedule of Assessments (Table 1) and as described in the Appendix. (Table 1).

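### The meal-test worksheet does not record how much of the drink was taken, so a smaller drink on Day 28 could not be told apart from a drug effect on the post-meal exploratory measures

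*Combined protocol and SAP*

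**What the plan says.** Section 8.2.7 fixes the test meal: "2x Ensure 8 oz. for a total of 16 oz., 66 grams carbohydrate (CHO), 440 calories". The 0-minute row of the Section 12 worksheet adds the time limit, "Give Ensure liquid meal (2x Ensure) Consume within 5 minutes", and then offers two blanks, "Start Time: _____ Stop Time". It has no entry for volume drunk, volume left or completion. Neither Section 8.2.7 nor Section 9 says what happens to a test in which the drink is not finished. Section 9.8 leaves the detail of exploratory analyses to a SAP.

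Subjects are "at least one year after sleeve gastrectomy or gastric bypass surgery" (Section 5). The test is done at run-in and on Day 28. The worksheet's row at 30 minutes before the meal reads "Study Drug Given IF SECOND MMTT", so dosing precedes only the later test. On what the drug may do, Section 6.9.1 says "ARD-101 may decrease appetite and subsequently change a subject's eating behavior by delaying gastric emptying". Section 2.2.2 reports lower food and water intake in rats within two hours of dosing. Section 4.1 describes an open-label study with no comparator.

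All MMTT measures are exploratory (Section 3.3).

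**The concern.** A meal test compares responses to the same load. Here one of the two tests follows a drug that may reduce appetite, and the load actually taken is not measured at either. A fixed volume on a short clock, in people with surgically reduced stomachs, makes an unfinished drink plausible. If it happens more often on Day 28, the before/after change mixes two things: the drug's effect on handling a meal, and the effect of a smaller meal. With no control arm, nothing else in the design separates them. A later analysis plan could not repair this, because it cannot recover a volume that nobody wrote down.

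The post-meal curves are the study's main evidence on metabolic response and on the proposed gut-hormone mechanism, so this affects how those results can be read.

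**Working it through.** **1. Reproduce the stated meal.** Inputs from Section 8.2.7: two bottles of 8 oz, 66 g carbohydrate, 440 kcal.

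- Volume: 2 × 8 = 16 oz, as stated. Per bottle: 66 / 2 = 33 g and 440 / 2 = 220 kcal.
- Rate implied by the worksheet: 16 × 29.57 mL per US fl oz ≈ 473 mL; 473 / 5 min ≈ 95 mL/min.

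**2. Which measures can be affected.** From the Section 12 timetable:

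| Time | Collected | Depends on amount drunk? |
|---|---|---|
| −80 to −50 min | Calorimetry #1 | No |
| −15 min | Glucose, insulin, C-peptide, FFA, gut hormones | No |
| −5 min | Glucose, insulin, C-peptide, cytokines, CRP, bile acids, ferritin, leptin, adiponectin | No |
| 15 to 240 min (nine draws) | Glucose, insulin, C-peptide | Yes |
| 60, 120, 180, 240 min | FFA | Yes |
| 120, 240 min | GLP-1, CCK, PYY, GIP, amylin, glucagon, ghrelin | Yes |
| 195 to 225 min | Calorimetry #2 | Yes |

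**3. Direction of the distortion if less is drunk on Day 28.**

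- Post-meal glucose, insulin and C-peptide would tend to be lower, which looks favourable.
- Meal-stimulated GLP-1, CCK, PYY and GIP would tend to be lower. That works against the rise in GLP-1 and CCK that Section 6.9.1 anticipates.
- Suppression of FFA and ghrelin would tend to be blunted.

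The net effect is therefore not in one direction.

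**4. Size.** The documents give no intake data, so every shortfall below is an assumption.

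Load for one subject = share drunk × 66 g (or × 440 kcal):

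| Share drunk | Carbohydrate | Energy |
|---|---|---|
| 90% | 59.4 g | 396 kcal |
| 75% | 49.5 g | 330 kcal |
| 50% | 33.0 g | 220 kcal |

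Fall in mean Day 28 load = (share of subjects not finishing) × (fraction they leave), if everyone finishes at run-in:

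| Subjects not finishing | Leave 25% | Leave 50% |
|---|---|---|
| 10% | 2.5% (1.65 g) | 5.0% (3.3 g) |
| 25% | 6.25% (4.125 g) | 12.5% (8.25 g) |
| 50% | 12.5% (8.25 g) | 25.0% (16.5 g) |

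With the 30 subjects of Section 4.1, the 10% and 50% rows are 3 and 15 subjects.

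**5. Equal shortfalls.** What matters for the change is the difference between visits: (share × fraction left on Day 28) − (share × fraction left at run-in). If these are equal, the difference in mean load is zero and the distortion largely cancels.

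**The case against.** The strongest reply is that nothing in the documents shows anyone leaving part of the drink, let alone leaving more on Day 28. Reduced stomach anatomy is present at both visits and does not by itself bias the change. Staff give the meal, a nurse initials each row and a physician signs the sheet. The stop time shows slow drinking, the post-procedure question on adverse events may catch overt intolerance, and Section 9.1.1 lists important deviations. All affected measures are exploratory. These points stand and limit the finding, but none of those records yields an amount, and no text makes an unfinished drink a listed deviation.

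Some stronger readings are tempting and are not supported:

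- *That a drug which cuts intake will appear to improve metabolism.* This needs a Day 28 shortfall that no text documents, and step 3 shows the direction is mixed.
- *That every MMTT measure is compromised.* Everything drawn before the meal, and the first calorimetry, is untouched.
- *That the protocol reports increased satiation for the study drug in people.* Section 2.1 says "While in an oral nutrient tolerance test, denatonium benzoate was shown to increase satiation". That is a different salt: ARD-101 is the acetate, and Section 2.4.2 states that no clinical efficacy study of it had been done.
- *That the response falls in proportion to the load.* The documents give no basis for this, so the figures above describe load only.

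**Conclusion.** The gap is real and worth closing, but it is a conditional one. Intake is not quantified at either test and no rule covers an incomplete drink. A Day 28 shortfall relative to run-in would therefore be confounded with the drug effect on the post-meal measures and could not be adjusted for afterwards. The size is unknown. Under the assumed range, with all subjects finishing at run-in, mean load falls by 2.5% to 25%; it is about nil if shortfalls are the same at both visits.

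The distortion could flatter glucose, insulin and C-peptide and could equally hide the expected hormone signal. Percent weight change, the secondary endpoints (adverse events, lipids, waist circumference, HbA1c) and fasting measures do not depend on it. The case for acting rests on the low cost and on the fact that unrecorded intake cannot be recovered later.

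**What to change.** Add a field *volume consumed (mL)* to the 0-minute row of the worksheet, completed at both MMTTs.

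State in the analysis plan that post-meal changes are reported in all subjects, with intake at run-in and Day 28 shown alongside. Add a sensitivity summary restricted to subjects whose two intakes agree, for example within 10%. That cut-off is a convention and should be fixed in advance. Label the summary as conditioning on a post-treatment variable: Day 28 intake may itself be changed by the drug, so the subset may favour subjects with the least appetite effect. For that reason it should not be the main analysis. The standard 16 oz meal can stay as it is at both visits; offering each subject the run-in volume on Day 28 would alter the fixed meal without ensuring that it is finished.

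The cost is one worksheet field and one extra table, with a smaller number of subjects in the sensitivity summary.
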